5.3 Secondary Endpoints

The same analysis as described above will be performed for freedom from durable loss of renal function at Days 14 and 90 and from improvement for freedom from durable loss of renal function as Days 14, 28, and 90.

Additional secondary endpoints include mSOFA over time, critical care and hospital stay parameters (ICU and ICU-free days, ventilator days and –free days, vasopressor days and –free days, and hospital length of stay (LOS)). Analyses for these endpoints will generally be descriptive, with emphasis on characterizing clinical effect sizes. Nominal p-values will be presented. Categorical outcomes will be described using counts and percentages with nominal p-values determined through chi-square or exact methods. Critical care and hospital stay endpoints will be described using non-parametric approaches including using concordance statistics to characterize clinical effect sizes and Wilcoxon rank sum tests to determine nominal statistical significance. Methods appropriate for time-to-event endpoints including survival and life-table methods will be used for time-to-recovery endpoints.

5.4 mSOFA

The Sequential Organ Failure Assessment score or SOFA was originally developed to track a patient's status during a stay in an intensive care unit (ICU)^{4,5}. Each of six organ systems are evaluated and assigned ordinal scores from 0 to 4. A total score is the sum of the component scores. For this study, the liver component is excluded from the sum score and the resulting sum score is referred to in this study as 'mSOFA'.

Several approaches will be taken to summarize changes over time and between treatment groups in the clinical scores as described below. Special handling of mSOFA scores includes the following:

1. If an individual organ score is missing but other scores for that day are non-missing, the organ systems that were not evaluated are assumed to be free of organ failure and given a value of zero when determining the sum score.
2. If all organ scores are missing for a specific day, the mSOFA total score from that day will be imputed using LOCF with the following exception, LOCF will not be performed after patient death.
3. When summarizing the individual organ scores apart from the mSOFA total scores, the same rules as above will apply.

Mean values and standard deviations (SD) for the SOFA and for the five specific organ components will be summarized over time with and without LOCF. Similarly, mean change scores from baseline (SD) will be summarized with and without LOCF.

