9.2.8 Acute Kidney Injury

During screening, it will be recorded whether the patient presented with Stage 2 or 3 AKI, or developed Stage 2 or 3 AKI within 48 hours after the suspected or confirmed diagnosis of abdominal infection, or surgical confirmation of NSTI. If a reference (baseline) serum creatinine value(s) is/are available from the past 12 months, the reference serum creatinine value(s) and date(s) obtained will be entered. If the subject does not have a reference serum creatinine value, it will be noted if the serum creatinine is ≥ 2.0 fold normal for age, race, and gender, and the length of the largest kidney by CT or renal ultrasound.

The stage of AKI (Stage 2 or 3) and how AKI was diagnosed (serum creatinine or urine output or both) will be recorded. The screening creatinine value prior to study drug administration as well as additional creatinine values from presentation or around (before) time of diagnosis of abdominal infection or NSTI should be entered. Urine output should be computed from presentation or around (before) time of diagnosis of abdominal infection or NSTI after accurate urine output is recorded. After study drug administration, urine output is collected while subject is in the ICU or step-down unit (or equivalent) with or without a Foley catheter in place through Day 7.

If receiving RRT, then the type of RRT and net fluid removed per RRT session will be collected through Day 28. Additional renal imaging or renal procedures (e.g., renal biopsy) performed as part of SoC through Day 28 will be entered in the eCRF.

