12.11.3 SOFA Scores

SOFA scores over time will be assessed as 1) observed cases, 2) LOCF, and 3) using MMRM.

Individually missing SOFA component values due to non-measurement are conventionally assumed as normal and this convention will be followed for this study.

LOCF will not be applied to missing SOFA scores after patient death in analyses that employ LOCF to describe mean values of time. Therefore, analysis of SOFA mean values using LOCF will focus on morbidity rather than mortality.

Mixed model repeated measures analyses will utilize implicit imputed values for all missing values including those subsequent to patient death.

In categorical analyses including formulation of the secondary effectiveness endpoint, total SOFA score at Day 14 ≤ 1 , LOCF is necessary to guarantee that every patient has a value at Day 14.

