3.10.6 Additional Processing Details

Based on experience gained through processing of AKI endpoints in the recently completed ATB-202 study, the following data processing convention will be employed.

- To account for renal replacement therapy (RRT), the exact dates on which the patient is on dialysis will be determined and compared to the exact date on which the labs were drawn for the creatinine sample. If the sample was drawn within 2 days from RRT start then it was excluded from all analyses.
- If the reference creatinine is greater than 1.4, then all available creatinine values obtained on Day 10 and after, including unscheduled visits, will be evaluated. If the maximum is 1.5x the minimum, then the reference creatinine is replaced by the MDRD.
- LOCF will be used for missing Day 14 creatinine starting from Day 10.
- LOCF will be used for missing Day 28 creatinine starting from Day 7.

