4.2 Secondary Effectiveness Endpoints

The secondary effectiveness endpoints for this study are:

- Freedom from durable loss of renal function at Day 14
- Freedom from durable loss of renal function at Day 90

Reference creatinine values, baseline AKI stage and percentage loss of eGFR at Days 14 and 90 will be determined through algorithmic determination (see details above). Percentage loss of eGFR determined algorithmically will be based on a comparison of eGFR at screening compared to an algorithmically determined reference creatinine value

- Resolution of organ dysfunction (organ resolution is defined as having a total mSOFA score of ≤ 1) at Day 14
- Resolution of specific organ dysfunction (defined as having an individual organ mSOFA score of ≤ 1) at Day 14
- Critical care and hospital stay parameters
 - Hospital length of stay
 - ICU length of stay
 - ICU-free days in 28 days
 - Days on ventilator
 - Ventilator free days in 28 days
 - Vasopressor days
 - Vasopressor free days in 28 days
 - Discharge status

- Patient survival at Days 14, 28 and 90.
- Presentation of Stages 1, 2, or 3 AKI (using the KDIGO criteria)
- **Stratifications involving Day 14 mSOFA \leq 1 vs Day 14 mSOFA \geq 2**
 - Compare critical care between Day 14 mSOFA \leq 1 vs Day 14 mSOFA \geq 2
 - Compare dose groups in those with Day 14 mSOFA \leq 1
 - Compare dose groups in those with Day 14 mSOFA \geq 2
- Among patients presenting with cardiovascular failure (shock), dose group predicting Day 14 mSOFA \leq 1
- Survival to Day 90 as a function of *freedom from durable loss of renal function at 28* (overall and by dose group)

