5.11.2 LOCF of Day 28 and Day 90 Creatinine

In order to determine the primary endpoint, freedom from durable loss of eGFR at Day 28, creatinine is necessary. Patients surviving to Day 28 or later but with missing Day 28 creatinine will have their Day 28 creatinine values determined through LOCF. The same procedure will be used for Day 90 Creatinine.

5.11.3 mSOFA Scores

mSOFA scores over time will be assessed as 1) observed cases, and 2) LOCF.

⁶ Cohen, J. (1988). *Statistical power analysis for the behavioral sciences* (2nd ed.). New York, Academic Press.

⁷ Kaplan EL and Meier P. Nonparametric estimation from incomplete observations, *Journal of the American Statistical Association*, **53**:457-481, 1959

⁸ Knickerbocker R. Intent-to-Treat Analyses. In: Chow S-C, ed. *Encyclopedia of Biopharmaceutical Statistics*. Marcel Dekker; 2000.

Individually missing mSOFA component values due to non-measurement are conventionally assumed as normal and this convention will be followed for this study.

LOCF will not be applied to missing mSOFA scores after patient death in analyses that employ LOCF to describe mean values of time. Therefore, analysis of mSOFA mean values using LOCF will focus on morbidity rather than mortality. Also, LOCF will not be used for missing mSOFA after Day 14.

In categorical analyses including formulation of the secondary effectiveness endpoint, total mSOFA score at Day 14 ≤ 1 , LOCF is necessary to guarantee that every patient has a value at Day 14. LOCF will not be performed after patient death.

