15.3 SOFA – Sequential Organ Failure Assessment Score

The following is provided in the Clinical Trial Protocol and is repeated here for convenience.

Can range from 0-24.

Value	0	1	2	3	4
Respiratory PaO₂/FiO₂¹	>400	≤400	≤300	≤200 with respiratory support	≤100 with respiratory support
Coagulation Platelets	>150	≤150	≤100	≤50	≤20
GI Total Bilirubin	<1.2	1.2-1.9	2.0-5.9	6.0-11.9	≥12.0
Cardiovascular²	No hypo- tension	MAP <70	Dopa ≤5 PE <100	Dopa > 5 Epi ≤ 0.1 NE ≤ 0.1 PE 100- 300	Dopa>15 Epi>0.1 NE>0.1 PE>300 VP>0.01
Neurology GCS	15	13-14	10-12	6-9	<6
Serum Creatinine OR Urine Output	<1.2	1.2-1.9	2.0-3.4	3.5-4.9 <500cc/ day	≥5.0 <200cc/ day

1. For patients on supplemental oxygen via nasal cannula, nasopharyngeal catheter or mask and for converting SpO₂ values to PaO₂ use the attached oxygen conversion tables.

2. Doses of dopamine (Dopa), epinephrine (Epi), norepinephrine (NE) are in micrograms/kg/min; phenylephrine (PE) is micrograms/min; vasopressin (VP) is U/min. Vasopressors must have been administered for at least one hour.

16 Appendix 7: Prior and Concomitant Medications

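### The SAP's mSOFA rules can count a patient on dialysis at Day 14 as having a resolved kidney

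*SAP*

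**What the plan says.** **Endpoint.** SAP 4.2 lists total mSOFA of at most 1 at Day 14 as a secondary endpoint. It also lists "Resolution of specific organ dysfunction", meaning a single-organ score of at most 1. mSOFA drops the liver, so five organs remain.

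**Renal item.** In the SOFA table (SAP 15.3, Protocol Appendix C) the row is "Serum Creatinine OR Urine Output". It has no line for RRT. Protocol 9.2.8 makes the seventh day the limit for collection after dosing: "urine output is collected while subject is in the ICU or step-down unit (or equivalent) with or without a Foley catheter in place through Day".

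**Missing organs.** Under SAP 5.4, when other organs were scored that day, "the organ systems that were not evaluated are assumed to be free of organ failure and given a value of zero". The third rule there extends this to single organs: "When summarizing the individual organ scores apart from the mSOFA total scores, the same rules as above will apply". SAP 5.11.3 words it more narrowly: "Individually missing mSOFA component values due to non-measurement are conventionally assumed as normal". Protocol 12.11.3 has the same convention for SOFA.

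**Creatinine near RRT.** SAP 3.10.6 says of creatinine samples: "If the sample was drawn within 2 days from RRT start then it was excluded from all analyses".

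**Dialysis elsewhere.** The primary endpoint requires freedom from dialysis (SAP 4.1), and Protocol 5.2 applies that endpoint at Day 14. AKI staging places the start of RRT in Stage 3 (SAP 3.10.2 and 15.1).

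**The concern.** Each rule is reasonable alone. Together they leave a patient whose kidney function is being replaced by a machine without a reliable way to register as having renal failure. The same patient can fail the Day 14 renal endpoint, sit in the top AKI stage, and count as a renal resolution in the mSOFA table on the same day.

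The kidney is the trial's indication, and planned or started RRT is one of the ways to qualify for entry (Protocol 6.1), so such patients are expected. The score feeds Tables 14.2.4.1 to 14.2.4.8 and the comparisons of Day 14 mSOFA at most 1 with at least 2 (SAP 4.2, 5.6, 8.5 and 8.8). If the drug reduces dialysis, the rule shrinks its apparent benefit on renal resolution. If the drug increases dialysis, the rule flatters it on that endpoint.

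**Working it through.** The plan gives no figure for this endpoint and no RRT rate, so there is nothing to reproduce. The check has two parts.

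**1. What score does a dialysed patient get at Day 14?** Applying the SOFA table and the SAP 5.4 rules:

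| Day 14 creatinine (mg/dL) | Renal score | Renal resolution (at most 1)? |
|---|---|---|
| treated as missing, other organs scored | 0 | yes |
| 1.0 | 0 | yes |
| 1.8 | 1 | yes |
| 2.5 | 2 | no |
| 4.0 | 3 | no |
| 5.5 | 4 | no |

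Two routes therefore lead to a false resolution.

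- *Route A, creatinine excluded.* Its reach depends on what RRT start means. If it is the start of the course, a Day 14 sample is lost only when the course began on Days 12, 13 or 14. If it is the start of each session, then on an assumed three-times-weekly schedule (for example Days 1, 3, 5, then 8) every day lies within 2 days after a session start, so every such Day 14 creatinine is lost. Route A also requires that a drawn but excluded value be treated as not evaluated (SAP 5.4), although SAP 5.11.3 speaks of non-measurement. The SAP settles neither point.
- *Route B, creatinine kept.* Any value that dialysis has brought below 2.0 mg/dL scores 0 or 1.

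**2. How much could this move the comparison?** Let

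- r = true renal resolution rate in an arm, with patients on RRT counted as not resolved;
- d = share of the arm alive and on RRT at Day 14;
- f = share of those patients whose renal score comes out as 0 or 1.

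Reported rate = r + f × d.

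Reported difference (active minus placebo) = (r_A − r_P) + f × (d_A − d_P).

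Inputs: 60 per arm (SAP 2.1.2). Assumed, because the documents do not give them: r = 70% against 55%, d = 10% against 20%. P-values are two-sided, from an uncorrected chi-square test.

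| f | Active | Placebo | Difference | p |
|---|---|---|---|---|
| 0 | 42/60 = 70% | 33/60 = 55% | 15 points | 0.09 |
| 0.5 | (42 + 3)/60 = 75% | (33 + 6)/60 = 65% | 10 points | 0.23 |
| 1 | (42 + 6)/60 = 80% | (33 + 12)/60 = 75% | 5 points | 0.51 |

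Varying the assumptions:

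- f = 0.2 with the same RRT rates: bias 0.2 × (10 − 20) = −2 points.
- Equal RRT use: d_A − d_P = 0, so the bias in the difference is zero for any f.
- RRT rates reversed (20% active, 10% placebo): bias of +2, +5 or +10 points for f = 0.2, 0.5 or 1.

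For total mSOFA of at most 1, the other four organs must also sum to at most 1 (or to 0 if the renal score is 1). If a share g of the falsely scored patients meets this, the bias is multiplied by g. With f = 1 and a 10-point RRT contrast it is 2 points at g = 0.2 and 5 points at g = 0.5 (both values of g assumed).

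**The case against.** The case against is substantial, and much of it limits the point.

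- *Day 14 creatinine will usually exist.* It is scheduled, and Protocol Appendix A requires it for SOFA on Days 1, 3, 7 and 14. A reader might infer that every dialysed patient is scored as having a normal kidney. The documents do not support that: a usable value of 2.0 or more scores 2 to 4.
- *The exclusion may not reach SOFA.* SAP 3.10.6 concerns processing of AKI endpoints, and 5.11.3 speaks of non-measurement. It also carries a missing Day 14 creatinine forward from Day 10, which might supply a value. But the exclusion is worded to cover all analyses, 5.4 has its own zero rule and does not refer to that carry-forward, the Day 10 visit occurs only if the patient is still in hospital, and the Day 10 value may itself be excluded or lowered by dialysis. The ambiguity stands, and Route B does not depend on it.
- *Urine output may be available.* Appendix A asks for the SOFA clinical parameters on Day 14, and a low volume would score 3 or 4. This may rescue some cases, but detailed collection is required only for Days 1 to 7.
- *Other organs share the defect.* The platelet item has no entry for transfusion, so the renal item is not unique. It is, however, the organ of the indication.
- *Dialysis is captured elsewhere.* It is failure in the primary endpoint, tabulated as a component, and RRT use is evaluated. A reader might infer that the trial would miss renal harm; it would not. The mSOFA analyses are generally descriptive, with nominal p-values.

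**Conclusion.** The concern holds in limited form. The rules as written can record a patient on dialysis at Day 14 as a renal resolution, contrary to the plan's own treatment of dialysis in the Day 14 renal endpoint and in AKI staging. How often depends on two undefined points (RRT start, and whether an excluded value is a non-measured one) and on how many dialysed patients have creatinine below 2.0 mg/dL.

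The direction is conditional. A reader might infer that the error always favours one arm; it does so only if RRT use among affected patients differs, and then toward the arm with more RRT. Under the assumed 10% against 20%, the loss is 0 to 10 of 15 points for renal resolution, and less for total mSOFA. The primary endpoint and its error rate are untouched. The plan should be corrected before unblinding, but no primary conclusion depends on it.

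**What to change.** In SAP 5.4 and 5.11.3:

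1. Count a patient receiving RRT at the Day 14 SOFA assessment as not resolved, for the renal component and for total mSOFA. Define receiving RRT so that a patient between sessions of a continuing course is included.
2. State that the zero rule for a missing organ does not apply to creatinine excluded under 3.10.6.
3. Define RRT start in 3.10.6 as course or session.
4. For the mean-score tables, prespecify a renal score for days on RRT, and report the as-measured score as a sensitivity analysis. The maximum score is one convention, matching the place of RRT in AKI staging. Nothing in the documents makes it the only choice.

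The cost is a few sentences and a small amount of programming. RRT data are collected through Day 28 (Protocol 9.2.8), and SAP 3.10.6 already requires exact dialysis dates. Reported resolution rates will be slightly lower.

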5.5 Assessment of Site to Site Variability in Relative Efficacy

Site to site variability in relative efficacy will be evaluated using a random effects meta-analysis approach using the R package *metafor* to implement the analysis. True effects are assumed to be normally distributed with mean μ and variance τ^2 . By imposing a specified distribution on the site-to-site variability, i.e. a normal distribution with mean μ and variance τ^2 , sensitivity to small sample sizes in individual sites is reduced and the parameters reflecting the magnitude of site-to-site variability are naturally derived. The quantitative measure of the magnitude of heterogeneity is I^2 . I^2 is the fraction of τ^2 that is due to effect size heterogeneity, as opposed to sampling variance. Fractions 25% and less are considered small. If there is significant site-to-site variability, the impact on this variability will be evaluated using a random effects logistic regression to test the null hypothesis that the likelihood of achieving freedom from durable loss of renal function at Day 28 is the same for treated and placebo patients accounting for a random site effect.

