2. PROTOCOL SYNOPSIS

Protocol Number	ATB-203
Protocol Title	Phase 3 randomized, double-blind, placebo-controlled, parallel-group study to evaluate the safety and efficacy of Reltecimod as compared to placebo in addition to standard of care in patients with sepsis-associated acute kidney injury (SA-AKI)
Location(s)	A multicenter study to be conducted in up to 90 qualified participating sites globally
Phase of Development	Phase 3
Study Population	
Patients with
 
• Suspected or confirmed abdominal infection (planned or completed surgical (laparotomy or laparoscopy) or interventional radiologic procedures for control of underlying abdominal infection within 24 hours of evaluation by medical personnel); or surgically confirmed necrotizing soft tissue infection (NSTI),• Requiring hospital admission to an intensive care unit (ICU) or step-down unit (or equivalent),• Total Sequential Organ Failure Assessment (SOFA) score ≥ 2, and• In whom the diagnosis of Stage 2 or 3 acute kidney injury (AKI; as defined by Kidney Disease Improving Global Outcomes (KDIGO) criteria) is established at initial presentation for medical evaluation; or up to 48 hours from the suspected or confirmed diagnosis of abdominal infection or surgical confirmation of NSTI.

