12.8 Assessment of Poolability Among Sites

Site poolability will be evaluated using a random effects meta-analysis approach using the R package *metafor* to implement the analysis⁴⁶. True effects are assumed to be normally distributed with mean μ and variance τ^2 . By imposing a specified distribution on the site-to-site variability, i.e. a normal distribution with mean μ and variance τ^2 , sensitivity to small sample sizes in individual sites is reduced and the parameters reflecting the magnitude of site-to-site variability are naturally derived. The quantitative measure of the magnitude of heterogeneity is I^2 ⁴⁷. I^2 is the fraction of τ^2 that is due to site to site differences in treatment effects (effect size heterogeneity), as opposed to sampling variance. Fractions 25% and less are considered small. If there is significant site-to-site variability, the impact on this variability will be evaluated using a random effects logistic regression to test the null hypothesis that the likelihood of achieving freedom from durable loss of renal function is the same for treated and placebo patients accounting for a random site effect. Poolability according to baseline demographic, disease severity status, and number of levels treated will be evaluated using descriptive stratified analyses.

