2.2 Randomization

120 patients will be recruited into the study and randomized to either 0.5 mg/kg Reltecimod or placebo in a 1:1 ratio. Randomization will be performed within site and according to the following stratification factors:

- **Acuity of AKI:** reflects whether or not AKI is diagnosed at time of presentation of abdominal infection or during the 48 hours following the suspected diagnosis of abdominal infection.
- **Subject Age:** ≥ 18 to ≤ 75 and > 75 to ≤ 85 years old
- Four computer-generated, blocked randomization lists will be provided for each site, one for each of the four strata defined on the basis of the 2 by 2 cross-tabulation of the two stratification variables. Within each block, half of the assignments will be to active drug and half to placebo, in random order. Block sizes will be varied.

The following provide details regarding randomization.

Biomedical Statistical Consulting will utilize software written in R Software (acceptable R versions > 3.1) to create the randomization schedule. The randomization inputs to this validated software are provided in Exhibit 1, with the exception of the final random seed utilized to generate the blinded randomization schedule. A draft randomization schedule will be generated with clearly marked “dummy” randomization treatment assignment (e.g., ‘DUMMY-Placebo’ and ‘DUMMY-Active’), and then exported to the necessary format for upload into the online randomization and study management system (RAVE Balance RTSM by Medidata Solution) administered by the Sponsor’s CRO (PharPoint Research, Inc.). The accurate upload of this “dummy” randomization schedule will then be verified by the unblinded study statistician, following the schedule provided by PharPoint Research, Inc. After verification, the process is repeated by the unblinded study statistician by rerunning the randomization software with updated seeds to determine the final (blinded) randomization schedule, with any “dummy-specific” notation removed. This final (blinded) randomization schedule is then uploaded to the online study management system utilizing the

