identical process verified through the “dummy” randomization schedule. A variable indicating the blinded treatment allocations will not be part of the clinical study data to be managed by the data management CRO to avoid risk of unblinding through inadvertent data transfer. Therefore, only blinded study data will be available to the blinded primary study statistician and blinded analysis staff. The randomization schedule parameters were set so that there would be an excess number of potential sites to over at least 60 sites in the US and at least 50 sites in France, Belgium and Netherlands. For every potential site, the maximum number of possible subjects was 30. Block sizes were randomly set to 2 or 4. Within each block, an equal number of allocations were made to the active and placebo groups. Separate randomization schedules were provided for each of 4 strata defined on the baseline of the acuity of AKI diagnosis and age category as described above.

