8.2 Evaluation of Site Heterogeneity in Primary Endpoint Treatment Effects

Table 14.2.1.4 provides comparisons of the percentages of patients achieving the primary efficacy endpoint by site, overall and by treatment group in the mITT analysis. If needed, site-to-site heterogeneity will be evaluated with these data using a random effects meta-analysis approach as described above.

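### At 120 patients over up to 90 sites, the site-level I-squared has almost no ability to show heterogeneity on the log-odds scale, so it should neither support pooling nor gate the site-adjusted model

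*SAP*

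**What the plan says.** SAP 5.5 and protocol 12.8 describe the same analysis. Treatment effects are estimated per site and combined in a random-effects meta-analysis in which true effects are assumed normal. I-squared is the measure of heterogeneity. The SAP continues: "Fractions 25% and less are considered small. If there is significant site-to-site variability, the impact on this variability will be evaluated using" a logistic regression with a random site effect. Both texts deal with small sites by stating that, under the normal assumption, "sensitivity to small sample sizes in individual sites is reduced". Both define I-squared as a fraction of tau-squared.

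SAP 8.2 plans a by-site table (14.2.1.4) and then makes the meta-analysis itself conditional: "If needed, site-to-site heterogeneity will be evaluated with these data using a random effects meta-analysis approach".

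On size, SAP 2.2 says "120 patients will be recruited into the study and randomized to either 0.5 mg/kg Reltecimod or placebo in a 1:1 ratio". The protocol synopsis allows "up to 90 qualified participating sites globally". The randomization schedule in SAP 2.2 held spare slots, "at least 60 sites in the US and at least 50 sites in France, Belgium and Netherlands", and adds: "For every potential site, the maximum number of possible subjects was 30. Block sizes were randomly set to 2 or 4". Each site has four lists, one per stratum.

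Neither document states the effect scale, a minimum site size or a rule for combining small sites. Neither says how one-arm or zero-cell sites are handled, or which test or level makes variability significant.

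**The concern.** A site can contribute a treatment effect only if it has patients in both arms, and its estimate is informative only if both outcomes occur. At one or two patients per site, most sites fail the first condition and nearly all fail the second. What remains is mostly continuity correction with a very large within-site variance, and in that setting I-squared falls to zero because there is no information.

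Two things are at stake. First, a small I-squared could be read as evidence that sites are poolable, which is the heading of protocol 12.8, when the statistic could hardly have shown anything else. Second, the model in SAP 5.5 is the only one the SAP names as accounting for site. Protocol 12.9 lists site as a logistic covariate, but SAP 5.7 replaces that list with the subgroup variables, which do not include site, and SAP section 1 says the SAP prevails. That one model therefore sits behind a screen with almost no power.

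**Working it through.** **The plan's own figures.** The documents give no operating characteristics for the heterogeneity analysis. The only related figure that can be reproduced is power. For 60 per arm, 75% against 50%, one-sided 0.05, the calculation gives 0.8897, against 0.890 in SAP Table 1. The success rates used below are therefore read as the plan intends.

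**Density.** 120/90 = 1.33 patients per site if every permitted site opens, and 120/110 = 1.09 over the schedule's minimum of 60 + 50 slots. With 120 patients spread evenly at random over 90 sites, the expected number of sites enrolling anyone is 90 × (1 − (89/90)^120) = 66. In simulation with four lists per site and blocks of 2 or 4, only about 25 of those have both arms, and they hold about 68 of the 120 patients.

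**Exact result for a site with one patient per arm (0.5 added to each cell).**
- Log-odds ratio: 0 if the two outcomes agree, otherwise ±ln(1.5 × 1.5 / (0.5 × 0.5)) = ±ln 9 = ±2.197.
- Variance: 1/1.5 + 1/0.5 + 1/0.5 + 1/1.5 = 5.333 in every case.
- Largest contribution to Q: 2.197² / 5.333 = 0.905.
- With k such sites, Q ≤ 0.905k while the degrees of freedom are k − 1. Since 0.905k ≤ k − 1 once k ≥ 1/(1 − 0.905) ≈ 10.5, from 11 sites on I-squared = max(0, (Q − df)/Q) is exactly 0 for any data.
- Risk difference: ±0.5 with variance 2 × 0.75 × 0.25 / 2 = 0.1875, so at most 0.25 / 0.1875 = 1.333 per site. I-squared then cannot exceed 1 − (k − 1)/(1.333k), which approaches 25% as k grows.

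**Simulation of the whole analysis.** Inputs from the documents: 120 patients, four lists per site, blocks of 2 or 4, 50% control success, 75% active success (odds ratio 3). Assumptions not in the documents: site log-odds ratios normal around ln 3, skewed enrolment across sites, 0.5 added to tables with a zero cell, one-arm sites dropped. A site standard deviation (SD) of 2 is extreme: 95% of site odds ratios lie between about exp(1.10 − 3.92) = 0.06 and exp(1.10 + 3.92) = 150.

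| Scale | Sites | Site SD | I-squared > 25% | Q test p < 0.05 |
|---|---|---|---|---|
| Log-odds ratio | 60–90 (21–23 with both arms) | 2 | at most about 0.5% | 0% |
| Log-odds ratio | 30 | 2 | 9% | 2% |
| Risk difference | 60–90 | 2 | 16–31% | – |
| Risk difference | 20–30 | 2 | 56–71% | – |
| Risk difference | 20–30 | 0 | 13–19% | – |

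**Sensitivity.** With even enrolment over 90 sites at SD 2, I-squared exceeds 25% in 0% of runs (log-odds) and 1.5% (risk difference). At the protocol's maximum of 320 patients over 90 sites, the figures are 0% and 20% (even), or 6.5% and 86% (skewed). With 10 sites of 12 they are 49% and 87%, and the risk-difference version exceeds 25% in 34% of runs with no heterogeneity.

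**Definition.** SAP 5.5 sets tau-squared as the variance of true site effects. The share of that quantity due to heterogeneity is always 100%. I-squared is the share of total variation in the observed site effects that is due to heterogeneity.

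**The case against.** The strongest reply is that the sparse density is a ceiling and not a plan. The 90 sites are a maximum, the schedule was deliberately oversized, one site may enrol up to 30, and no expected enrolment per site is given. That stands, and it limits the finding to low site density.

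A reader might infer that I-squared will be zero whatever the truth, or that sites look poolable by construction. The documents do not support this. It is exact only for one-against-one sites on the log-odds scale with a 0.5 correction, and the plan fixes none of these. The primary hypothesis and its confidence interval are stated as a difference in proportions, so the risk-difference scale is a fair reading, and there I-squared can exceed 25% often. This changes the form of the problem without removing it, because the answer then depends on an unstated scale and can err in either direction.

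A reader might also infer that the follow-up model will never run. The trigger is undefined significance and not I-squared above 25%, so that cannot be read from the text. What can be said is that a Q-test reading of the trigger is never met at 60 to 90 sites on the log-odds scale.

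The SAP heading no longer speaks of poolability, and Table 14.2.1.4 will show the sparse counts whatever I-squared says. Both are true and reduce the harm. Finally, a model with only a random site effect adjusts for site but does not estimate variation in the treatment effect, so running it always does not by itself answer the heterogeneity question. That also stands, and the fix allows for it.

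**Conclusion.** The concern holds in a limited form. At 120 patients over 60 to 90 sites on the log-odds scale, which is the natural one given the logistic follow-up, the planned analysis has almost no ability to show heterogeneity. I-squared exceeds 25% in at most about 0.5% of trials under extreme heterogeneity, and the Q test is never significant. At 30 sites the figures are 9% and 2%. On the risk-difference scale the outcome depends heavily on site density and can mislead upwards.

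It follows that a small I-squared cannot support poolability. The statement that sensitivity to small sites is reduced is not supported at this density. The random-site model should not depend on this screen. The definition of I-squared is wrong in both documents.

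These results rest on the assumed spread of enrolment, the 0.5 correction, dropping one-arm sites and normal site effects. It would be wrong to infer that the trial's main result is at risk: the primary test is an unadjusted chi-square, and no success criterion depends on I-squared. This is a low-cost improvement to a supportive analysis.

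**What to change.** In SAP 5.5 and 8.2, and in protocol 12.8:

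1. Remove the 25% benchmark and the conditional trigger, and with them the site-level meta-analysis.
2. If I-squared is mentioned at all, define it as the share of total variation in observed site effects due to heterogeneity.
3. Always fit the random-site logistic model, labelled as a supportive, site-adjusted estimate of the treatment effect.
4. Let a treatment-by-region estimate with its confidence interval (US against France, Belgium and the Netherlands) carry the question of consistency. Region is not among the subgroups in SAP 5.6, so it must be added.
5. Keep Table 14.2.1.4 as a descriptive by-site display.

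The cost is wording and one model run unconditionally, on data already collected, settled before unblinding. The downside is that no formal site-level heterogeneity statistic is reported and the region contrast will be imprecise. Assuming an even split (30 per arm per region) at 75% against 50%, the standard error of the difference between regional risk differences is √(2 × (0.75 × 0.25/30 + 0.5 × 0.5/30)) = 0.171. The 95% interval is then about ±0.33, and wider if the split is uneven. It should be reported as descriptive only.
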